9.3.6. Version 6.0: 04 June 2021

Overall reason for Version 6.0: The overall reasons for Version 6.0 were to clarify that male subjects must use contraception and that all subjects must use contraceptive measures from the time consent is signed until 30 days after treatment discontinuation and to add an appendix of prohibited medications.

Section	Version 6.0/Update	Reason/ Rationale
Protocol	The version number and date were updated throughout. Editorial revisions (eg, typographical error, punctuation, tenses, and abbreviations) were incorporated to provide clarity. The synopsis was updated to be consistent with changes in the protocol.	Update
Section 4.3	Revision to exclusion criterion 2 to increase aspartate transaminase and alanine transaminase to $\geq 3 \times$ upper limit of normal and remove exception for underlying diseases Revision of exclusion criterion 9 to specify that “strong” cytochrome P450 inhibitors or inducers are prohibited Revision of exclusion criterion 10 to specify that male subjects must also use contraception and addition of requirement for use of contraception for all subjects from the time consent is signed until 30 days after treatment discontinuation Addition of exclusion criterion 11 to indicate that subjects with comorbidities that may confound study results (eg, fat malabsorption syndrome, other mitochondrial disorders) in the opinion of the investigator will be excluded	Update and clarification
Section 7.1	Removal of the option of choosing the time for the post-dose sample and specify 4 hours postdose to be done with the 4-hour ECG (for subjects weighing <10 kg) Removal of hematology panel at the Screening Visit Revision of chemistry laboratory assessments to include only alanine aminotransferase, aspartate aminotransferase, and creatinine at the Screening Visit Added electroencephalogram at Week 24	Update
Section 7.1.2.1 Section 7.1.2.8 Section 7.3	Removal of the option of choosing the time for the post-dose sample and specify 4 hours postdose to be done with the 4-hour ECG (for subjects weighing <10 kg)	Clarification
Section 7.1.2.8	Added electroencephalogram at Week 24	Update
Section 7.1.3	Removed all timepoints except for 4 hours postdose for PK at Weeks 48 and 72	Clarification
Section 7.4.2	Revision of total blood volume to be drawn over the course of the study and addition of weight-based volumes Addition of cross-reference to Table 2 and revision of cross-reference from Section 7.1.2.7 to Section 7.1.2.8	Update and Clarification
Section 7.5.10	Revision to specify that male subjects must also use contraception and addition of requirement for use of contraception for all subjects from the time consent is signed until 30 days after treatment discontinuation	Clarification
Section 7.5.12	Revision of section title to indicate “Safety Reporting Requirement” Addition of text to indicate notification by PTC to investigators of any new or emerging safety information	Clarification
Section 9.3.4	Revision of item numbers 4 through 18 due to previously missing number 4	Clarification
Appendix 1	Addition of appendix of prohibited medications	Update

9.3.7. Version 7.0: 06 January 2022

Overall reason for Version 7.0: The overall reason for Version 7.0 was to incorporate feedback from health authorities.

Section	Version 7.0/Update	Reason/ Rationale
Protocol	The version number and date were updated throughout. The synopsis was updated to be consistent with changes in the protocol. Editorial revisions (eg, typographical errors, punctuation, tenses, and abbreviations) were incorporated to provide clarity.	Update
Section 4.2	Inclusion criterion #2 was updated to include subjects <21 years of age. Inclusion criterion #6 was updated to "Documented medical history of epilepsy associated with mitochondrial disease for at least 6 months prior to screening except for subjects who are <2 years of age at the time of screening (Subjects <2 years of age can be considered for enrollment if all other screening criteria are met due to the potential for rapid progression in these subjects) ".	Update
Section 4.3	Exclusion criterion #3 which read, "INR \geq ULN at time of screening", was revised to read "INR >ULN at time of screening".	Update
Section 5.1.1 Section 7.1	It was corrected that weights ending in decimals ≥ 0.5 (instead of >0.5, as stated previously) should be rounded up to the next whole number for dosing calculation.	Update
Section 7.1 Section 7.1.2.8	It was specified that informed consent for subjects entering the long-term extension phase would be completed at Week 24.	Update
Section 7.1.3	It was clarified that EEG is to be collected at Week 72, as already specified in Table 2.	Clarification
Section 7.4.1	The text was updated to specify that weight could also be collected in lb and height could also be collected in inches.	Update
Section 7.4.2	The total volume of blood collected as written in V6.0 is incorrect and has now been corrected.	Update

9.3.8. Version 8.0: 27 May 2022

Overall reason for Version 8.0: The overall reason for Version 8.0 was to remove "a minimum number of 6 subjects" per mitochondrial disease subtype category and clarify the blinding of the investigators, study subjects, and sponsor during the placebo-controlled and open-label phases of the study.

Section	Version 8.0/Update	Reason/ Rationale
Protocol	The version number and date were updated throughout. The synopsis was updated to be consistent with changes in the protocol. Editorial revisions (eg, typographical errors, punctuation, tenses, and abbreviations) were incorporated to provide clarity. Relevant updates to the study personnel and approval signatures pages were made.	Update
Section 3.1.2	The following text was removed: "A minimum of 6 subjects (approximately) will be allocated to category 1), 2), and 3), respectively."	Update

Section	Version 8.0/Update	Reason/ Rationale
Section 5.3	The blinding of the investigators, study subjects, and sponsor was clarified with the following text: “The investigators, study subjects, and sponsor will be blinded as follows: the sponsor will be blinded to the randomized treatment until the study is unblinded after all subjects complete the placebo-controlled phase; subjects and investigators remain blinded to the treatment received during the placebo-controlled phase until after all subjects complete the open-label phase. An independent Data Safety Monitoring Board (DSMB) will monitor the study until completion of the placebo-controlled phase of the study.”	Clarification
Section 7.1	The following clarifying text was added to footnote “g” of Table 2 : “If a subject cannot perform a urine pregnancy test at any timepoint, a serum pregnancy test should be performed.”	Clarification
Section 7.1.2 Section 7.1.3	The following clarifying text was added to the relevant timepoints: “If a subject cannot perform a urine pregnancy test, a serum pregnancy test should be performed.”	Clarification
Section 7.4.3	The following text was added for clarification: “If a subject cannot perform a urine pregnancy test at any timepoint, a serum pregnancy test should be performed.”	Clarification

APPENDIX 1. PTC743-MIT-001-EP PROHIBITED MEDICATION LIST

Table 7: PTC743-MIT-001-EP Prohibited Medication List

Prohibited Medications	Examples
Anticoagulants	
 • heparin • warfarin • aspirin • clopidogrel • apixaban • dabigatran • edoxaban • enoxaparin • rivaroxaban
CYP3A4 strong inducers	
 • apalutamide • carbamazepine • enzalutamide • mitotane • phenytoin • rifampin • St. John's wort
CYP3A4 strong inhibitors	
 • boceprevir • cobicistat • danoprevir and ritonavir • elvitegravir and ritonavir • grapefruit juice (any grapefruit product) • indinavir and ritonavir • itraconazole • ketoconazole • lopinavir and ritonavir • paritaprevir and ritonavir and (ombitasvir and/or dasabuvir) • posaconazole • ritonavir • saquinavir and ritonavir • telaprevir • tipranavir and ritonavir • telithromycin • troleandomycin • voriconazole • clarithromycin • idelalisib • nefazodone • nelfinavir
Investigational medications for MIT-E	
Idebenone	

Prohibited Medications	Examples
Artisanal (non-Epidiolex cannabidiol)	

Abbreviations: CYP3A4, cytochrome P450 3A4

Note: This list is neither comprehensive, nor final. In general, study subjects should not be taking any strong CYP3A4 inhibitors or inducers, anticoagulants, or any investigational medications.

MELAS	mitochondrial encephalomyopathy, lactic acidosis, and stroke-like episodes
mt-aaRS2	mitochondrial aminoacyl tRNA synthetase 2 genes
PCH6	pontocerebellar hypoplasia type 6
PedsQL	Pediatric Quality of Life Inventory™
PK	pharmacokinetics
POLG	polymerase subunit gamma
PP	per-protocol
PT	prothrombin time
PT	preferred term
PTT	partial thromboplastin time

Abbreviation	Term
QTc	corrected QT interval
SAE	serious adverse event
SAP	statistical analysis plan
SOC	system organ class
TEAE	treatment emergent adverse event
TFL	table, figure, and listing
TID	ter in die (Three times a day)
VAS	visual analogue scale
WHO	World Health Organization

1. INTRODUCTION

The purpose of this statistical analysis plan (SAP) is to describe the procedures and the statistical methods that will be used to analyze data and report results for PTC743-MIT-001-EP (Protocol version 8.0 dated on 27 May 2022). Table, figure, and listing (TFL) specifications are contained in a separate document.

There will be two database locks for this study. The first database lock (soft lock) will occur when all subjects complete the double-blind treatment period. The final database lock will occur when all subjects have completed the open-label treatment period.

This SAP outlines the statistical methods that will be used to analyze the data collected during the double-blind period and will be finalized and approved prior to the first database lock. A separate SAP for the open-label treatment period will be finalized and approved prior to the final database lock.

1.1. Study Design

This study is a parallel-arm, double-blind, placebo-controlled trial, with a screening phase that includes a 28-day run-in phase to establish baseline observable motor seizure frequency. The 28 days immediately prior to the Baseline Visit is considered the run-in phase. Screening is followed by a 24-week randomized double-blind placebo-controlled phase during which subjects will be randomized to receive either vatiquinone at a dose of 15 mg/kg if body weight <13 kg, and 200 mg if body weight \geq 13 kg, 3 times daily (TID) or placebo TID. Following completion of the randomized double-blind phase, all subjects will be offered entry into a long-term extension phase (48 weeks) during which they will receive open-label treatment with vatiquinone and then a safety follow-up, as needed.

Subjects who meet eligibility criteria will be randomized to vatiquinone or placebo in 1:1 ratio, with approximately 30 subjects in each arm. The randomization included stratification by disease subtype including: 1) Alpers/DNA polymerase subunit gamma (POLG); 2) Leigh syndrome; 3) mitochondrial encephalomyopathy, lactic acidosis, and stroke-like episodes (MELAS), and 4) other genetically confirmed mitochondrial disease secondary to mitochondrial mutation. These strata were decided prior to initiation of enrollment based on the fact they are three mitochondrial disease subtype with relatively high prevalence (though still quite rare) and seizures as a prominent aspect of disease pathology.

1.2. Study Objectives

1.2.1. Primary Objective

The primary objective of the study is to demonstrate the effect of vatiquinone on reduction in observable motor seizure frequency in subjects with genetically confirmed mitochondrial disease, as assessed by a seizure diary.

1.2.2. Secondary Objectives

Secondary objectives of the study are to:

- Demonstrate the effects of vatiquinone on seizure-related emergency room visits and hospitalizations.
- Demonstrate the effects of vatiquinone on occurrence of status epilepticus.
- Demonstrate the effects of vatiquinone in monthly total seizure count.
- Demonstrate the effects of vatiquinone in responder rate in motor and non-motor seizures.
- Demonstrate the effects of vatiquinone on number of rescue antiepileptic medications used.
- Demonstrate the effects of vatiquinone on health-related quality of life (using the Care-Related Quality of Life-7 Dimensions [CarerQoL-7D] questionnaire).
- Demonstrate the effects of vatiquinone on occurrence of seizure clusters.
- Demonstrate the safety of vatiquinone as assessed by drug-related serious adverse events (SAEs), drug-related adverse events (AEs), and dose modifications.

1.2.3. Exploratory Objective

The exploratory objective of the study is to demonstrate the effects of vatiquinone on health-related quality of life (using the Pediatric Quality of Life Inventory™ [PedsQL] questionnaire).

1.3. Endpoints

1.3.1. Primary Endpoint

The primary efficacy endpoint of the study is the percent change from baseline in frequency of observable motor seizures per 28 days during the double-blind phase.

1.3.2. Secondary Endpoints

Key secondary efficacy endpoints of the study are as follows:

- Number of disease-related hospitalization days.
- Occurrence or recurrence of status epilepticus.

Other Secondary endpoints are as follows:

- Number and percent of subjects with disease-related in-patient hospitalization/emergency room visits.
- Number of disease-related in-patient hospitalization admissions/emergency room visits.
- Percent change from baseline in total seizure frequency per 28 days of all types.
- Each of the CarerQoL-7D dimensions will be summarized descriptively by visit for double-blind period and open-label period respectively.
- Number of rescue seizure medications.

- Number of seizure clusters as defined by “too many to count” entries in the seizure diaries.

1.3.3. Exploratory Endpoint

The exploratory efficacy endpoint of the study is health-related quality of life as measured by the PedsQL questionnaire.

1.3.4. Safety Endpoints

Safety endpoints include both clinical and laboratory variables.

1.3.4.1. Clinical Variables

- All AEs and SAEs
- Drug-related SAEs
- Drug-related AEs

1.3.4.2. Physical Examination, Vital Signs, 12-lead Electrocardiogram (ECG) and Electroencephalogram (EEG)

- Vital signs include height, weight, temperature, respiratory rate, systolic blood pressure, diastolic blood pressure, heart rate and oxygen saturation.
- Physical examination includes general appearance, skin, head, eyes, ears, nose, throat, neck (including thyroid), lymph nodes, chest, heart, abdomen, and extremities.

1.3.4.3. Laboratory Variables

- Hematology includes erythrocytes, leukocytes, and platelets.
- Coagulation includes PT and PTT reported as international normalized ratio (INR) units.
- Serum Chemistry includes liver function, renal function, electrolytes, general chemistry and lipids.
- Urinalysis includes pH, protein, glucose, ketones, blood and bilirubin.

1.4. Sample Size Determination

It is planned to randomize 30 subjects per arm in this study. Sixty subjects (30 subjects in each treatment group) will provide 80% power to detect a 40% treatment difference with common standard deviation of 50% at a two-sided significance level of 0.05 based on the Wilcoxon Rank-Sum Test. The 40% treatment difference is based on 10% and 50% decrease in the placebo treatment group and vatiquinone treatment group, respectively, for percent change from baseline in motor seizure frequency per 28 days.

2. STUDY POPULATIONS AND PERIODS FOR ANALYSIS

This is a basket trial of mitochondrial disease enrolling several specific, ultrarare, and potentially heterogeneous disease subtypes where refractory epilepsy is a significant and highly morbid aspect of disease pathology. Due to this, this trial will be analyzed overall and in predefined disease subtypes.

Considering the patient population currently enrolled into the study we are pre-specifying three specific mitochondrial disease subtypes of interest in whom we seek to understand treatment effect independent of those recorded in the overall population. These disease subtypes are:

- Leigh syndrome
- Pontocerebellar Hypoplasia Type 6 (PCH6)
- Mitochondrial aminoacyl tRNA synthetase (mt aaRS2) disorders inclusive of PCH6

All analyses planned for the overall population will be repeated in these disease subtypes.

2.1. Study Populations

2.1.1. Intention-to-Treat Population

Intention-to-treat (ITT) population will include all subjects who were randomized and received at least one dose of treatment. In the event that a subject received study drug different from the one to which he/she was randomized, the subject's efficacy data will be analyzed "as randomized". ITT Analysis population will be used in the statistical analyses of the efficacy endpoints.

2.1.2. Safety Population

Safety population will include all subjects who were randomized and received at least one dose of treatment. In the event that a subject received study drug different from the one to which he/she was randomized, the subject's safety data will be analyzed "as treated". The Safety Analysis population will be used in the statistical analyses for safety.

2.1.3. Per-Protocol Population

The per-protocol (PP) population will include subjects in the ITT population who do not have any important protocol deviations leading to exclusion from the PP population.

The protocol deviations that may have major effect on efficacy which will lead to exclusion of the subjects from per-protocol population include:

- Subjects that had significant inclusion and exclusion criteria violations.
- Subjects that had protocol deviations which may impact effectiveness of study treatment.
- Subjects that received study treatment different from the randomized treatment throughout the double-blind period.
- Subjects with <80% of valid days entered in the seizure diary during the run-in period.

- Subjects with non-compliance to study drug administration with compliance <80% and >120%.
- Subjects with less than 80% compliance in the seizure diary of valid days entered in the diary during either run-in period or during double-blind period.
- Subjects who change anti-seizure medication or increase dose of anti-seizure medication not related to weight or begin/change in ketogenic diet during the study during double-blind period.
- Subjects that discontinued study treatment due to withdrawal, noncompliance, and death during the double-blind period.

All protocol deviations leading to exclusion from the PP population will be reviewed and approved by the study team prior to treatment unblinding. The list of PP population subjects will be finalized prior to treatment unblinding.

This population will be used as supportive efficacy analysis for the primary efficacy endpoint.

2.2. Study Periods

2.2.1. Double-blind Period

Double-blind period for efficacy or safety endpoints is defined as the period from randomization or first dose date, respectively, to:

- the last dose of double-blind study drug if the subject continues to the open-label extension period
- or
- the last study visit if the subject does not continue to the open-label extension period.

Double-blind period will be used for summarizing efficacy and safety endpoints.

2.2.2. On-vatiquinone Period

On-vatiquinone period is defined as the period from the first dose of vatiquinone, regardless of double-blind or open-label vatiquinone, to the end of the study.

On-vatiquinone period will be used for summarizing safety endpoints.

3. GENERAL CONSIDERATIONS

3.1. Definition of Estimand for the Primary Objective

The primary estimand of the study is the percent change from baseline in frequency of observable motor seizures per 28 days during the double-blind period. The attributes of the primary estimand are defined in [Table 1](#).

Summary Measure:

The median of the variable of interest will be estimated for each treatment group. The difference in median of the variable of interest between two treatment groups will be estimated using Hodges-Lehmann estimator and 95% confidence interval (CI). The p-value will be computed from ranked ANCOVA detailed in [Section 5.1.2](#).

Table 1: Primary Estimands

Population	Variable	Intercurrent Events	Population-level Summary	Analysis
The population of subjects <21 years of age with genetically confirmed mitochondrial disease as defined by the protocol inclusion/exclusion criteria.	Percent change from baseline of motor seizure frequency per 28 days during the double-blind period.	
Rescue medication status: Study treatment will not be modified based on rescue medication status in line with a treatment-policy strategy.
 
Emergency room visits and hospitalization: The days which patient has emergency room visits, or is hospitalized, will not be excluded from the calculation of primary endpoint as long as the diary is available for such days in line with a treatment-policy strategy.
 
Changes in anti-seizure medications: Study treatment will not be modified and patient's will not be excluded as a result of changes in anti-seizure medications that are a medical necessity and in line with a treatment-policy strategy
 
Early termination or discontinuation: Data will be used as collected
	Treatment difference between vatiquinone and placebo in percent change from baseline to Week 24 will be estimated using the ANCOVA based on rank transformed data.	Primary analysis for primary efficacy endpoint

Abbreviations: ANCOVA, analysis of covariance

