5.1.2. Primary Analysis

For primary analysis, both the motor seizure frequencies per 28 days in the pre-randomization period as well as the percentage change in motor seizure frequencies per 28 days in the double-blind period will be rank transformed separately.

The analysis of covariance (ANCOVA) will then be conducted on this rank transformed data with treatment, and stratifying factor and the ranked pre-randomization phase seizure frequency per 28 days as a covariate. P-values will be computed between active and placebo treatment groups.

Due to an expected irregular distribution of seizure frequency, median will be the primary statistic of interest for the primary endpoint. The difference in median of the percent change from baseline between the two treatment groups will be estimated using Hodges-Lehmann estimator along with 95% CI for understanding the treatment effect size.

The stepwise approach to estimate the median difference of percent change using Hodges-Lehmann estimator is:

- a. derive the seizure frequency per 28 days for baseline (BL) and double-blind (DB) period.
- b. calculate the percent change from baseline as $100 \times (DB - BL)/BL$.
- c. apply the below SAS code of PROC NPAR1WAY nonparametric model to generate Hodges Lehmann Estimator:

```
*** Hodges Lehmann Estimator;  
proc npar1way data=<dataset name> HL ;  
  class <treatment variable name>;  
  var <percent change from baseline variable name>;  
  ods select HodgesLehmann;  
run;
```

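### The Hodges-Lehmann effect is described as a difference in medians, Table 1 attributes it to rank ANCOVA, and its interval omits the covariates behind the primary p-value

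*SAP*

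**What the plan says.** The summary-measure text of SAP 3.1 names the median in each arm and then says: "The difference in median of the variable of interest between two treatment groups will be estimated using Hodges-Lehmann estimator". SAP 5.1.2 says the same of the endpoint itself: "The difference in median of the percent change from baseline between the two treatment groups will be estimated using Hodges-Lehmann estimator". The code given there ("apply the below SAS code of PROC NPAR1WAY nonparametric model to generate Hodges Lehmann Estimator") has one grouping line, "class <treatment variable name>", with no stratum and no baseline term.

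The p-value has another source: "The p-value will be computed from ranked ANCOVA detailed in" SAP 5.1.2. That model contains "treatment, and stratifying factor and the ranked pre-randomization phase seizure frequency per 28 days as a covariate". After the merging in SAP 3.8 the stratum has two levels, Leigh syndrome and Other.

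The population-level summary in Table 1 of SAP 3.1 says that the treatment difference in percent change "will be estimated using the ANCOVA based on rank transformed data".

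Protocol 8.4.2 says only that the Hodges-Lehmann estimator and its interval are shown to convey effect size. It does not call the estimate a difference in medians. SAP 3.6 declares the study positive if the primary p-value is below 0.05.

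**The concern.** Three quantities are treated as one.

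- **Difference in medians:** the median of one arm minus the median of the other.
- **Hodges-Lehmann estimate:** the median of all differences between one subject on vatiquinone and one on placebo. If the arms have the same shape and differ by a shift, or if both are symmetric, this equals the difference in medians. Otherwise it need not. Percent change cannot fall below -100% and has no upper bound, and SAP 5.1.2 itself expects an irregular distribution.
- **Rank ANCOVA coefficient:** a difference in adjusted mean ranks. It is not in percentage points, so it cannot be the percent-change difference that Table 1 describes.

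The Hodges-Lehmann interval is the planned between-arm effect size in percentage points for the primary endpoint. It is built without the covariates that the decisive test uses. If those covariates predict outcome, the interval is less precise than it could be, and a report could show p<0.05 beside an interval containing 0, or the reverse. The SAP does not say how such a result would be presented. The same pairing carries into most of the sensitivity analyses in SAP 5.1.3, total seizures in 5.2.2.1, and the subtype repeats in Section 2.

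**Working it through.** **Inputs from the documents.** 30 per arm, two-sided alpha 0.05, planning effect 40 points (medians taken here as -10% and -50%), SD 50 (Protocol 8.2, SAP 1.4); test and interval as in SAP 5.1.2. **Assumed, because the documents give no figure:** distribution shape, covariate correlations, and 40% of subjects in the Leigh stratum.

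**Planned power first.** For a Wilcoxon test under normal data, P = Φ(40/(50√2)) = 0.714. Noether's formula gives Φ((0.714 - 0.5)·√(3·60) - 1.96) = 82.0%. This is close to the protocol's 81% and the SAP's 80%, so the planning inputs are read correctly.

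**Step 1: size of the labelling gap.** Take double-blind/baseline ratios as lognormal with medians 0.9 and 0.5 and common log-SD s. The true difference in medians is -40. The pooled SD of percent change is √((90² + 50²)/2)·exp(s²/2)·√(exp(s²) - 1), where the first factor is 72.8. The Hodges-Lehmann parameter is the simulated median of pairwise differences.

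| log-SD | pooled SD | Hodges-Lehmann | gap from -40 |
|---|---|---|---|
| 0.5 | 44 | -38 | 2 |
| 0.55 | 50 | -37.6 | 2.4 |
| 0.7 | 74 | -36 | 4 |
| 0.9 | 122 | -34 | 6 |
| 1.1 | 205 | -31 | 9 |

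At the planning SD the gap is about 2.4 points, against a median interval width of about 42 points. The larger lognormal gaps need SDs of 2.4 times (122/50) and 4.1 times (205/50) the planned one.

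Shape matters as well as spread. Take a responder mixture with 55% responders against 25%, median ratios 0.2 for responders and 1.05 for non-responders, and log-SD 0.35. It has a difference in medians of -58.2 and a Hodges-Lehmann value of -28.7, a gap of 29.5 points. Under a normal shift the two agree on average, but within one trial they differ with an SD of about 7.5 points.

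**Step 2: agreement of p and interval.** Each simulated trial (4,000 per row, normal data, SD 50) compares the rank-ANCOVA p-value with the unadjusted Hodges-Lehmann 95% interval. Correlations are the absolute values for baseline/stratum with outcome. Entries are % of trials.

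| Effect | Correlations | p<0.05 | CI excludes 0 | p<0.05, CI includes 0 | p≥0.05, CI excludes 0 | Disagree |
|---|---|---|---|---|---|---|
| 40 | 0/0 | 82.9 | 83.7 | 1.2 | 2.0 | 3.2 |
| 40 | 0.3/0.2 | 87.1 | 83.2 | 5.9 | 2.0 | 7.9 |
| 40 | 0.5/0.3 | 94.3 | 84.9 | 10.5 | 1.1 | 11.6 |
| 25 | 0/0 | 44.9 | 46.1 | 2.1 | 3.4 | 5.5 |
| 25 | 0.3/0.2 | 49.9 | 44.6 | 8.8 | 3.5 | 12.4 |
| 25 | 0.5/0.3 | 58.8 | 45.7 | 17.5 | 4.4 | 21.9 |
| 0 | 0/0 | 4.5 | 4.1 | 0.9 | 0.5 | 1.4 |
| 0 | 0.3/0.2 | 4.8 | 5.1 | 1.4 | 1.7 | 3.1 |
| 0 | 0.5/0.3 | 4.3 | 4.4 | 2.1 | 2.1 | 4.2 |

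A separate normal-data simulation at 40 points gave about 2-11%, so about 2-12% is a fair statement.

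Lognormal data with log-SD 0.55 and the planned effect (400 trials each) gave 1.8%, 0.5% and 3.5% for no, moderate and strong covariate effects. The standard error of the last is √(0.035·0.965/400) = 0.9 points. That scenario also adds a stratum effect of 0.5 log units, which lifts the total log-SD to √(0.55² + 0.5²·0.24) = 0.60, so its spread is somewhat above plan. At log-SD 0.9 with strong covariates the figure was 16%. The responder mixture gave 7.0%.

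**Step 3: validity of each piece.** Rank-ANCOVA rejection under no effect was 4.3-4.8%. The unadjusted interval covered its own target in 92-97% of trials. An interval from inverting the adjusted rank test covered in 93-97%.

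**The case against.** A good deal can be said for the plan as written. SAP 5.1.2 gives the formula and the code, so no analyst could compute a different statistic. SAP 3.1 already reports each arm's median, so a reader can form the actual difference. At the planning SD the lognormal labelling gap is small beside the interval width. In every worked example with an effect on skewed data, Hodges-Lehmann is smaller in size than the difference in medians, so there the label would not flatter the drug. With no or moderate covariate effect, adjusted and unadjusted intervals are nearly equally wide (41 against 41.5 points, and 40 against 42.3). An inverted-test interval itself assumes a shift. All of this stands, and it limits the size of the point. It does not make the label or Table 1 correct, and the mixture shows that a spread near the plan's does not by itself keep the gap small.

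A reader might infer more: that the primary result is unreliable, that type I error is inflated, or that the trial has no rule for a conflict between p and interval. The documents do not support this. SAP 3.6 gives the interval no part in the decision, the adjusted rank test holds its level in simulation, and the unadjusted interval is valid for what it estimates. What is missing is only guidance on reporting a conflict.

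**Conclusion.** The point holds as a fault of description and effect-size reporting. The label in SAP 3.1 and 5.1.2 is not true in general, Table 1 credits a percentage-point difference to a model that yields mean ranks, and the interval omits covariates that the decisive p-value uses.

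The labelling gap is about 2.4 points for lognormal data at the planning SD and larger for wider or mixed distributions. At the planned 40-point effect, p and interval disagree in about 2-12% of trials under normal data with SD 50. Under lognormal data at that SD it is under 2% with covariates of no or moderate value, and low single figures if they are strong. About 20% is reached only with a smaller effect or wider spread together with strongly prognostic covariates. When covariates are prognostic, the commoner conflict is p<0.05 with an interval that includes 0.

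None of these rates is a prediction, since the documents state neither the distribution nor any covariate correlation. The change is worth making, but nothing in the trial's decision depends on it.

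**What to change.** 1. In SAP 3.1, 5.1.2 and Table 1, call the estimate the Hodges-Lehmann location shift (median of pairwise between-arm differences). Make Table 1's population-level summary match, and name rank ANCOVA as the test only.
2. Add a point estimate and 95% interval that use the same stratum and ranked baseline as the p-value. One way is to invert the test: keep every shift d for which the rank ANCOVA of (percent change - d × treatment) gives p≥0.05. At d = 0 this is the primary test, so the interval and p agree on zero by construction.
3. Keep the unadjusted Hodges-Lehmann estimate and the arm medians as supportive, with a sentence on how any conflict with p will be reported.
4. Carry the wording through to the analyses that reuse the primary method.

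The cost is SAP text and a short macro, with no new data, sample size or alpha. The downside is that the adjusted interval rests on the shift model that Hodges-Lehmann already implies.
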